Screening: Once the patient signs the consent form, a screening period of up to two weeks will initiate to determine the patient's eligibility for the study, prior to entering the randomization phase. Only eligible patients will enter the randomization phase.

Randomized Phase: Monthly infusions (of either B or P) will start at week 0 and continue every four weeks until week 36 (10 months) for the “randomized” phase of the study. In addition, there will be a “loading dose” at week 2 (per drug [IND] specifications). The loading dose will consist of either Belimumab or Placebo (saline) in the B or P treatment arms, respectively.

Open Label Phase: Monthly infusions (of B) will start at week 40 and continue every four weeks until week 64 (6 months) for the “open-label” phase of the study.

A comprehensive evaluation of the patient (Physical exam and history, vital signs, AEs, CBC and metabolic panel, GGT, myoglobin, pregnancy test, urinalysis, ESR, CRP, CPK, immunoglobulins, muscle and health evaluations, physician global assessment, patient self-assessments, serum level sampling) will be conducted at weeks 0, 8, 16, 24, 32, 39-40, 52, 64. A less comprehensive set of evaluations (vital signs, AEs, CBC and metabolic panel, GGT, pregnancy test) will be conducted at weeks 2, 4, 12, 20, 28, 36, 40, 44, 48, 56, 60. A detailed schedule of visits and procedures is outlined in appendix A.

A telephone follow-up conversation will also be conducted at weeks 72 and 84.

Optional Exploratory Studies

Blood based biomarker assessments and blood based RNA assessments will be performed on stored samples for consenting patients at Northwell Health only. See Appendix A (schedule of events).

b. Randomization:

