3. an increased dose of corticosteroid before study week 8 and did not return to $<25\%$ above the baseline dose by week 12.

Endpoints:

1. **Primary Endpoint:**
 - a. Response rate at 40 weeks defined as percentage of patients meeting definition of improvement (DOI) in IIM patients treated with belimumab and standard therapy compared to the percentage of patients meeting DOI treated with placebo and standard therapy.
2. **Secondary Endpoints:**
 - a) Incidence of flares: flare rates during 40 weeks randomization period in patients with IIM treated with belimumab and patients treated with placebo and at week 64 in each group.
 - b) Time to achieve initial improvement defined as the time to reaching DOI.
 - c) Duration of improvement; quantified as the time from achieving improvement to the time of worsening or a disease flare. (Time from 1st DOI to 1st DOW or disease flare event). This will be based on the subset of subjects who achieve improvement.
 - d) Percent change in muscle enzyme levels (CPK and myoglobin) from baseline to week 40 and 64 in each respective group
 1. $<20\%$ reduction: no response
 2. 20-70% reduction: partial response
 3. $>70\%$ reduction: complete response
 - e) Percent change in manual muscle assessment (MMT-8) from baseline to week 40 and week 64 in each respective group.

- 1. <20% reduction: no response
- 2. 20-70% reduction: partial response
- 3. >70% reduction: complete response
- f) Percent change in prednisone dose from baseline to week 40 and week 64 in each respective group
- g) Proportion of subjects, among those on steroids at baseline, able to reduce the prednisone dose to ≤ 5 mg daily at week 40 and week 64 in each respective group.
- h) Flare rate in placebo group during the 40 week randomized treatment phase as compared to that group in the 20 week open label phase.
- i) Serious adverse event and adverse event rates
- j) Changes in B cell populations from baseline to week 40 and week 64
- k) Changes in autoantibody titers from baseline to week 40 and week 64
- l) Changes in immunoglobulin concentrations from baseline to week 40 and week 64

Inclusion Criteria:

Subjects enrolled in the study must meet the following inclusion criteria:

- 1) Adults ≥ 18 years of age
- 2) Have a diagnosis of:
 - a. definite or probable dermatomyositis (DM) by modified Bohan & Peter criteria or

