
1. For specific aim 1, the two treatment arms [B vs. P] will be compared with respect to the proportion of subjects who respond to treatment at 40 weeks (improvement according to definition), using either a chi-square test or Fisher’s exact test, as appropriate.
2. For specific aim 2, either a chi-square test or Fisher’s exact test, as appropriate, will be conducted to compare the proportion of subjects who had any flares during the 40-week randomized phase. For this analysis, each subject will be categorized at the end of 40 weeks as having had one or more flares or not having had any flares. In addition, we can also examine the total number of days that a subject had a specific flare during the course of the 40-week treatment, and compare the two treatment arms using the ‘Incidence density ratio’ method.
3. For specific aim 3, standard methods for survival analysis will be carried out. The Kaplan-Meier (KM) product limit method will be used to estimate overall “time-to-achieve (initial) response/improvement”. Ninety-five percent confidence intervals will be calculated using Greenwood’s formula for computing the standard error. Subjects who have not achieved improvement as of week 40 will be considered ‘censored’ for the event (event=improvement/response).
4. For specific aim 4, similar methods as indicated for specific aim 3 will be conducted. The analysis for this aim will be limited to the subset of subjects in each treatment arm who show improvement at anytime during the randomized phase of the trial. A subject who has not flared/worsened/relapsed as of week 40 will be considered ‘censored’ for the event (event=flare/relapse).
5. For specific aims 5, 6, 7, 9 and 10, each of the outcome variables of interest (uncensored continuous or categorical) will be analyzed separately, using a mixed model approach to repeated measures analysis of variance (MMRMANOVA) with the main effects of treatment arm (B vs. P), Disease type (PM vs DM), Disease Severity (Severe vs. Less Severe) and time (baseline vs. 40 weeks). If feasible, statistical interactions between

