There will be no formal interim analyses or formal statistical stopping rules. However, statistical summaries of adverse event rates using 95% exact confidence intervals will be provided to the data safety monitoring board as need. During regular bi-annual meetings the data safety monitoring board will evaluate the overall rate of adverse events and unanticipated problems. Upon review the group will determine whether there are any changes needed to the anticipated benefit-to-risk assessment and if the study should continue. The results of these regular meetings will be recorded and disseminated to the other participating clinical sites. Safety data will be collected in the form of adverse events (AEs), serious AEs (SAEs) and laboratory parameters (e.g., hematology, chemistry, etc.). AEs will be recorded with the date of onset, severity, relationship to study drug, and disposition. AEs will be translated into a standard classification system such as COSTART or MedDRA. AE data will be summarized according to incidence rates, by treatment arm and by whether or not the AE was treatment related. AEs will be summarized using descriptive statistics and tabulated according to treatment group for each strata. The AE report will be descriptive, rather than inferential.

SAMPLE SIZE CONSIDERATIONS

We plan to enroll 30 evaluable patients with 15 in each of two treatment arms [B vs. P].

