From available trials in IIM, there is an observed placebo effect of 0%-40% at 12 weeks^{9,10} and 0% at 52 weeks⁹. These results demonstrate that the placebo response rate at 40 weeks can be very variable. One clinical study looking at rituximab in myositis was the first prospective, double-blind, randomized trial in myositis and the largest clinical trial ever performed in the inflammatory myopathies¹⁶. This trial employed a unique design; subjects were divided into two groups: early-start and delayed-start of rituximab. Overall, 83% of enrolled subjects (with severe refractory disease) met the DOI by the end of the trial, despite lack of statistical significance between groups. An alternate double-blind, placebo-controlled trial of etanercept (50 mg subcutaneously weekly for 52 weeks) where 16 subjects were randomized showed that: all 5 subjects receiving placebo were treatment failures (median time to treatment failure: 148 days)¹⁷. In contrast, 5 of 11 subjects in the etanercept arm were successfully weaned off prednisone; the median time to treatment failure in this group was 358 days ($p = 0.0002$). This data shows that for myositis trials, placebo response is often close to 0%. In order to achieve a clinically meaningful difference between study treatment arms, the response rate of the treatment group would need to be at least 50%.

We hypothesize (optimistically) the response rate at 40 weeks in the placebo arm to be 5%. We further assume that a magnitude of difference of 45% would be clinically meaningful (this corresponds to a 50% response rate in the Belimumab arm).

Based on the assumption that a difference of 45% in response rates at 40 weeks between Placebo and the investigational agent, Belimumab, would be clinically meaningful, then, a two group chi-square test ($\alpha=0.05$, two sided test) will yield 80% power to detect a difference between the Placebo arm week 40 response rate of 5% and a Belimumab-treated arm week 40 response rate of 50% (Odds ratio=19) when the sample size in each group is 15, assuming the dropout rate is 0%.

Table 1 below shows the sample size requirements for various pairs of (hypothesized) 40-week response rates and assumptions on what would be a clinically meaningful difference between treatment arms. Corresponding sample sizes are provided for the specified range of parameters. Calculations were based on a two-sided chi-square test to achieve 80% power ($\alpha=0.05$).

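### Greenwood-based Kaplan-Meier intervals for time to improvement can collapse and under-cover with 15 patients per arm if few placebo patients improve; name a small-sample method that works at zero events

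*Combined protocol and SAP*

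**What the plan says.** The secondary endpoint is "Time to achieve initial improvement defined as the time to reaching DOI". Under Statistical Methods, item 3, the Kaplan-Meier method "will be used to estimate overall “time-to-achieve (initial) response/improvement", patients without improvement are censored at week 40, and "Ninety-five percent confidence intervals will be calculated using Greenwood’s formula for computing the standard error". Item 4 (duration of improvement) adds that "similar methods as indicated for specific aim 3 will be conducted", restricted to patients who improved.

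The text fixes the standard error only. It does not say on which scale the interval is formed, what is reported when an arm has no event, whether the limits belong to the curve or to the median, or whether the word overall means one pooled curve or one curve per arm. The Specific Statistical Aims are framed as comparisons of the two arms, which makes by-arm curves the natural reading.

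Sample Size Considerations plans 15 evaluable patients per arm, no dropout, and hypothesizes "the response rate at 40 weeks in the placebo arm to be 5" per cent, against 50% on belimumab. It also cites placebo effects of 0% to 40% at 12 weeks.

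**The concern.** Greenwood's formula is a large-sample variance. With no events it equals zero, and with very few events the normal approximation around it is poor. The plan itself expects few placebo responders in an arm of 15. In that setting the report could show a placebo improvement estimate of 0% with a 95% interval of 0% to 0%, which claims certainty that 15 patients cannot give. The same happens early on any curve: before an arm's first event, the interval has zero width by construction, in either arm. At stake is whether the error bars on a secondary efficacy display can be taken at face value.

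**Working it through.** **Inputs.** n = 15 per arm, dropout 0%, placebo 5% and belimumab 50% at week 40 (Sample Size Considerations). Full evaluations "will be conducted at weeks 0, 8, 16, 24, 32, 39-40, 52, 64" (Study Procedures and Schedule), so there are five post-baseline chances to meet the definition by week 40. The documents give no rate for ever improving by week 40, so that rate p is an assumption and is varied.

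**The plan's own figure.** No interval width or coverage is stated. The sample size does reproduce: with mean rate 0.275, n = [1.96·√(2·0.275·0.725) + 0.8416·√(0.05·0.95 + 0.50·0.50)]² / 0.45² = (1.238 + 0.459)² / 0.2025 = 14.2, rounded up to 15. Power at 15 is 82.3%.

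**Collapse.** With no censoring before week 40, Greenwood's variance there is S(1−S)/n, where S is the proportion not yet improved. It is 0 when nobody has improved, which has probability (1−p)^15. At p = 5% this is 0.95^15 = 46.3%.

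**Coverage at p = 5% (true S = 0.95).** Probabilities of 0, 1, 2, 3, 4 and 5 improvers are 0.4633, 0.3658, 0.1348, 0.0307, 0.0049 and 0.0006.
- Plain: with 1 improver, 0.933 ± 1.96·√(0.933·0.067/15) = 0.807 to 1.060. That is −6% to 19% improved, so it runs below zero. The interval contains 0.95 for 1 to 4 improvers and misses for 0 or for 5 or more: 0.3658 + 0.1348 + 0.0307 + 0.0049 = 53.6%.
- Log: also covers with 5 improvers, giving 53.7%.
- Log-log: covers only with 1 or 2 (with 3 its upper limit is 0.931), giving 50.1%. It is undefined at zero events, counted here as a miss.
- Exact (Clopper-Pearson): covers for 0 to 3, giving 99.5%. With 0 of 15 its lower limit is 0.025^(1/15) = 0.782, so up to 21.8% improved remains compatible with the data.

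**Other rates**, week 40, no dropout:

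| n | ever improved | no event | plain | log | log-log | exact |
|---|---|---|---|---|---|---|
| 15 | 5% | 46.3% | 53.6% | 53.7% | 50.1% | 99.5% |
| 15 | 10% | 20.6% | 79.2% | 79.4% | 73.9% | 98.7% |
| 15 | 15% | 8.7% | 89.6% | 91.2% | 85.1% | 98.3% |
| 15 | 20% | 3.5% | 81.5% | 83.2% | 90.4% | 98.2% |
| 15 | 40% | 0.05% | 93.9% | 90.8% | 96.1% | 98.5% |
| 15 | 50% | 0.003% | 88.2% | 93.7% | 93.7% | 96.5% |
| 30 (pooled) | 27.5% | 0.006% | 92.5% | 93.7% | 95.0% | 96.2% |

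The pooled rate is (5% + 50%)/2. The dip at 20% comes from discreteness: the plain interval with 1 improver starts at 0.807 and just misses 0.80, and that outcome has probability 15·0.2·0.8^14 = 13.2%.

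**Simulation.** Kaplan-Meier curves over the five visits (20,000 runs, p = 5%) gave 46.3% collapsed and 53.6% plain coverage. With an assumed 20% dropout these became 51.1% and 48.7%.

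**Item 4.** At p = 5% the expected number of placebo improvers is 15·0.05 = 0.75, and the chance of none or one is 0.463 + 0.366 = 83%.

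**The case against.** A reader might infer that the plan chose the plain, untransformed interval. It did not: log and log-log intervals also use Greenwood's standard error, and the scale is left open. This does not rescue the plan, since all three fail at zero events, but the fault is the missing zero-event method and not a wrong choice of scale.

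A reader might also take 46% as what the plan itself predicts for this endpoint. The 5% is the assumed response status at week 40 for the primary endpoint. Time to improvement counts the first success at any of five visits, so ever improving is at least as frequent. Given the planned 5% and no dropout, 46% is an upper bound. The cited 12-week placebo range reaches 40%, where plain coverage is 94%. This objection stands and limits the size of the problem.

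If overall means a pooled curve, coverage at week 40 is adequate. That is a possible reading, though the aims compare arms.

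The interval is descriptive, no decision rule uses it, and the primary comparison already allows Fisher's exact test. That also stands. Finally, exact limits are not the only repair: with complete follow-up a score (Wilson) interval covers 96.4% at 5%, and between 91.5% and 98.2% over the rates from 5% to 50% that were examined. It is a binomial interval, however, and does not by itself handle censoring.

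**Conclusion.** The point holds in limited form. For a by-arm curve with 15 patients, intervals based on Greenwood's standard error have no usable width before the first event, and at week 40 they under-cover when few patients have improved. Plain coverage is 54% if 5% ever improve, 79% at 10%, 90% at 15% and 82% at 20%. The problem largely disappears by 40%. These figures assume one arm, the week-40 point and no dropout, and the rates above 5% are assumptions because the documents give none for ever improving.

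The coverage figures do not carry over to item 4, whose denominator is the improvers only. With none or one in the placebo arm, no interval method is informative. Nor do the documents support reading this as a threat to the trial's main conclusion: the primary test, its alpha and the sample size do not use these intervals. It is a cheap improvement to a secondary, descriptive result.

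**What to change.** Replace the Greenwood sentence in item 3 with wording such as: *Curves will be estimated separately by treatment arm. Pointwise 95% confidence limits will use the beta product confidence procedure, which equals the Clopper-Pearson interval at visits with no prior censoring.* This gives a usable interval at zero events and matches the exact intervals that the Safety Data section already specifies for adverse event rates.

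For item 4, add that the individual durations will be listed when an arm has too few improvers for a curve, with the minimum number fixed in advance.

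The cost is two SAP sentences, a check that the analysis software offers the method, and wider, conservative limits (coverage of 96.5% to 99.5% in an arm of 15 over the rates examined, without dropout). Nothing else in the design changes.

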The Biostatistics Unit at the Feinstein Institute for Medical Research [BU-FIMR] will develop a web based randomization plan for the study. A randomization schema will be generated by the BU-FIMR for each participating site using the method of permuted blocks. Subjects will be randomly assigned in a 1:1 ratio to either Belimumab or Placebo, according to two stratification variables, namely, disease type (Polymyositis or Dermatomyositis) and disease severity (severe or less severe). The Biostatistics Randomization Management System (BRMS) is a secure, HIPAA-compliant, web-based application that allows investigators to randomize subjects into randomized clinical trials (RCTs) using their personal computer. The BRMS allows for multi-center, stratified, and single/double blinded RCTs, using permuted blocks. Randomization notifications are automatically sent to the PI and other authorized personnel. Using BRMS is a good way to maintain compliance in RCTs.

c. Stratification:

Randomization will be according to the two important stratification variables: disease type (Polymyositis vs. Dermatomyositis) and disease severity (severe vs less severe) and will occur at week 0 (first infusion). The number of immunosuppressive agents used by the patient over the last year (corticosteroids are not included) will be used as a surrogate of disease activity: one or less IS agent over last year versus more than 1 IS agent over last year.

d. Blinding:

This is a double-blind study; both the investigator and the patient will be blinded to the treatment assignment in the randomized phase of the trial. At the end of the 40 week randomized treatment phase all subjects will start the 20 week open label phase and therefore the drug will be dispensed in the unblinded fashion.

For each study site, there will be a designated unblinded research coordinator (URC) and a blinded research coordinator (BRC). The URC will be responsible for obtaining randomization assignments from the BU-FIMR and will oversee the preparation of infusions prior to drug administration. The BRC will be responsible for coordinating patient visits and administration or the infusion (infusion will be masked and not identifiable through any physical characteristics such as color or consistency, as the drug is of a powder form mixed in saline solution).

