The Biostatistics Randomization Management System (BRMS) is a secure, HIPAA-compliant, web-based application that allows investigators to randomize subjects into randomized clinical trials (RCTs) using their personal computer. The BRMS allows for multi-center, stratified, and single/double blinded RCTs, using permuted blocks. Randomization notifications are automatically sent to the PI and other authorized personnel. Using BRMS is a good way to maintain compliance in RCTs.

Statistical Considerations

SPECIFIC STATISTICAL AIMS

The primary objective of the study is to compare subjects in the Belimumab group and subjects in the placebo group with respect to response (improvement) at week 40.

The specific aims of the study are to compare the two treatment arms (Belimumab vs. Placebo [P vs. B]), during the 40-week randomized phase of the study, with respect to the following:

1. Response at week 40.
2. Flare rates during the 40-week treatment period.
3. Time-to-achieve (initial) improvement during the 40-week randomized phase of the study
4. Duration of improvement during the 40-week randomized phase of the study, among those who achieved improvement (this is essentially a time-to-flare/relapse analysis from the time that you achieved improvement)
5. Change in muscle enzyme levels (CPK, myoglobin) from baseline to week 40
6. Change in MMT-8 from baseline to week 40
7. Change in prednisone dose from baseline to week 40

8. Proportion of subjects able to reduce prednisone dose to ≤ 5 mg at week 40
9. Change in B cell populations, immunoglobulin levels and BLys levels from baseline to week 40.
10. Change in autoantibody titers from baseline to week 40.
11. Rates of SAEs and AEs experienced

STATISTICAL METHODS

All subjects will be analyzed according to the intention-to-treat [ITT] principle. A subject will be considered evaluable and will be included in the intention-to-treat analysis if he/she received at least the first five of the planned infusions during the randomized phase of the study. Subjects who do not get the first five infusions will be considered ‘drop-outs’. It should be noted that the study protocol calls for patients remaining on their treatment assignment. However, adjustments in dosages of medications used in their ‘standard care’ are permitted during the first 8 weeks. Analyses that take into account the actual treatment received (e.g. accounting for compliance, etc.) will be carried out as a secondary analysis (per protocol [PP] analysis).

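### Duration of improvement (aim 4) is listed as a between-arm comparison but analysed only in improvers, a post-randomisation subset that may be very small on placebo

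*Combined protocol and SAP*

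**What the plan says.** Under Specific Statistical Aims, eleven aims are introduced as being to "compare the two treatment arms (Belimumab vs. Placebo [P vs. B]), during the 40-week randomized phase of the study". Aim 4 is the duration of improvement, and its own wording confines it to patients who achieved improvement.

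Secondary endpoint c) defines duration as the time from the first time the definition of improvement (DOI) is met to the first worsening or flare, and adds: "This will be based on the subset of subjects who achieve improvement".

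Statistical Methods, item 4, repeats the restriction: "The analysis for this aim will be limited to the subset of subjects in each treatment arm who show improvement at anytime" in the randomised phase. Patients without a flare or worsening by week 40 are censored. On method it says: "For specific aim 4, similar methods as indicated for specific aim 3 will be conducted". Item 3 describes Kaplan-Meier estimation with Greenwood intervals and names no between-arm test. A closing sentence of the section adds multivariable logistic and Cox models for the outcomes above if feasible, with a caution about sample size.

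Under Sample Size Considerations, each arm has 15 evaluable patients, and the plan hypothesises "the response rate at 40 weeks in the placebo arm to be 5" per cent, against 50% on belimumab. No rate is given for improvement at any time before week 40.

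**The concern.** DOI is the basis of the primary endpoint, and the trial is sized on treatment raising it from 5% to 50% at week 40. A group selected because it met DOI is therefore selected on a consequence of treatment. Placebo improvers are those who improve without the drug. Belimumab improvers are a mixture of those patients and others who improve only because of the drug. The two groups can differ in prognosis even though the arms were balanced at randomisation.

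A difference in duration between improvers could thus appear with no drug effect on durability, or a real effect could be hidden or reversed. With few placebo improvers, the comparison may also carry almost no information. No analysis of duration in all randomised patients is planned to set beside it.

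**Working it through.** **Inputs.** From Sample Size Considerations: 15 per arm; week-40 response 5% on placebo and 50% on belimumab; two-sided chi-square test, alpha 0.05, 80% power, no dropout; a cited placebo effect of 0% to 40% at 12 weeks. From Study Procedures & Assessments: after Day 0, the clinical core set measures are scheduled at weeks 8, 16, 24, 32 and 40 of the randomised phase.

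**The plan's own figure.** n = [1.960 × √(2 × 0.275 × 0.725) + 0.842 × √(0.05 × 0.95 + 0.50 × 0.50)]² / 0.45² = (1.238 + 0.459)² / 0.2025 = 14.2, so 15 per arm, as stated. Power is 82.3% at 15 and 79.3% at 14.

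**Placebo improvers.** With any-time improvement rate p, the number of improvers is Binomial(15, p), the expected number is 15p, and P(none) = (1 − p)^15.

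| Any-time placebo rate p | Expected improvers | P(none) | P(at most 1) |
|---|---|---|---|
| 5% (equal to the week-40 rate) | 0.75 | 46% | 83% |
| 10% (assumed) | 1.5 | 21% | 55% |
| 20% (assumed) | 3.0 | 4% | 17% |
| 40% (assumed; top of the cited 12-week range) | 6.0 | 0.05% | 0.5% |

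A patient who meets DOI at week 40 has met it at some time, so any-time improvement cannot be rarer than week-40 response. Given the plan's 5%, the first row is a lower bound for the expected number and an upper bound for the chance of none. On belimumab, 15 × 0.50 = 7.5 improvers are expected on the same basis.

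**What such counts can show.** With 1 placebo and 8 belimumab improvers, the smallest one-sided permutation p-value is 1/9 = 0.11, so an exact test cannot reach 0.05. With 6 and 8 improvers, all of whom relapse, approximate log-rank power at a hazard ratio of 0.5 is Φ(√(14 × 6/14 × 8/14) × 0.693 − 1.960) = Φ(−0.68), about 25%. This approximation is rough at such counts.

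**Selection (assumed figures, no drug effect on duration).** Suppose 5% of patients would improve on either arm and a further 45% only on belimumab.
- If the first group relapses at 20% and the second at 50%, placebo improvers relapse at 20% and belimumab improvers at (0.05 × 0.20 + 0.45 × 0.50) / 0.50 = 47%. The drug appears to shorten improvement.
- If the risks are 50% and 20%, the figures are 50% and (0.05 × 0.50 + 0.45 × 0.20) / 0.50 = 23%. The drug appears to prolong it.

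The improvers' data alone cannot show which case applies.

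**The case against.** The restriction is disclosed and consistent: the endpoint definition, the aim and the methods all limit duration to improvers. A reader might infer that the aim promises one comparison and the methods deliver another. The documents do not support that, because aim 4 itself carries the restriction.

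A reader might also infer that the plan expects a nearly empty placebo group and an analysis that usually cannot be run. That goes too far. The 5% is a week-40 rate, the plan gives no any-time rate, and it calls placebo response very variable. The plan does also say that placebo response in myositis trials is often close to 0%, so a very small group is a real possibility, though not a stated expectation.

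Item 4 names no between-arm test, Cox modelling is conditional on feasibility, and aims 1, 2 and 3 cover response, flare and time to improvement without restriction to improvers. This limits the consequences. It does not make aim 4 descriptive: the plan calls the adverse event report descriptive in so many words, but does not say so here, and aim 4 stays on the list of arm comparisons.

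Censoring at week 40 is not a defect in itself. It leaves late improvers with little follow-up, but it is specified and Kaplan-Meier estimation accommodates it.

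**Conclusion.** The point holds as a weakness of one secondary comparison. The arms are to be compared on duration in groups formed after randomisation by an outcome that treatment is expected to change, so a difference between them cannot be read as an effect of belimumab on durability. This conclusion does not depend on the placebo rate: at 40% the group is not empty, but the selection remains.

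The size of the placebo group does depend on the rate. The expected number runs from 0.75 (the bound if the 5% is right) to 6 (any-time rate assumed at the top of the cited range), and the chance of none from 46% to 0.05%.

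It is tempting to add that placebo improvers must have the best prognosis, so that the bias works against the drug. Nothing in the documents establishes this, and the illustration gives bias in both directions. The primary analysis is unaffected.

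**What to change.** 1. In Statistical Methods item 4, state that the Kaplan-Meier duration among improvers is descriptive, with no between-arm test, and exclude it from the Cox models.
2. For the between-arm comparison, use all randomised patients: weeks in improvement without flare from week 0 to week 40, derived from the scheduled core set assessments and scored 0 for patients who never improve. Compare the arms with a rank or permutation test that accounts for disease type and severity. Name the analysis set explicitly, since the plan's evaluable set requires the first five infusions.
3. Add a short derivation rule covering 8-weekly visits, improvement that is lost and regained, and dropout.

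**Cost.** SAP wording and a derived variable with its rule. Visits, treatment and sample size do not change. The measure answers a different question, because it mixes onset with durability; the improver-only curve therefore stays as a supplement. It also overlaps with aim 1 and will have many ties. If any-time rates equalled the week-40 assumptions, about 14.25 placebo and 7.5 belimumab patients, 21.75 of 30, would score 0. Thirty patients over four strata also leave small cells, so the stratified test should be specified in advance.
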